**Effective**

Version: 2.0

associated with inflammation or discolouration. The early occurrence of subcutaneous nodules at the injection site (within 3–6 weeks after treatment) may be minimised by adhering to proper dilution and injection techniques. Delayed occurrences of subcutaneous nodules at the injection site (within 1–14 months post injection) have been reported with sometimes a prolonged duration of up to 2 years. Improper injection techniques such as superficial placement, excessive amount of product or incorrect reconstitution may lead to appearance of papules or nodules at the injection site. Massaging the treatment area to ensure proper distribution of the product may minimise the appearance of such papules or nodules.

For nodular areas or late granuloma formation, in some cases, they resolved spontaneously or following treatment with multiple intralesional injections of corticosteroids and/or antineoplastic agents (e.g. 5-fluorouracil). Surgical excision of the nodules was sometimes required when they were larger in size, occurring in difficult anatomical regions (e.g. lower eyelid) or persisting after other treatments.

This product must not be injected intramuscularly or intravascularly. Localised superficial necrosis and scarring may occur after injection in or near vessels. It is thought to result from the injury, obstruction, or compromise of blood vessels. Special caution should be taken if the patient has undergone a prior surgical procedure in the planned treatment area. Areas with limited collateral blood flow has an increased risk of ischaemia. Aspiration prior to injection is recommended.

Unintentional introduction of soft tissue fillers into the vasculature in the face may lead to embolisation, occlusion of the vessels, ischaemia, necrosis or infarction at the implant site or in the area supplied by the blood vessels affected. Rare but serious adverse events include temporary or permanent vision impairment, blindness, cerebral ischaemia or cerebral haemorrhage leading to stroke, skin necrosis, and damage to underlying facial structures. Immediately stop the injection if any of the following symptoms occurs, including changes in vision, signs of a stroke, blanching of the skin, or unusual pain during or shortly after the procedure. Patients should receive prompt medical attention and possibly evaluation by an appropriate health care practitioner specialist, should an intravascular injection occur.

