1.1 Background

1.1.1 Study design

This is a randomized, multi-center, evaluator-blinded, no-treatment controlled study of Sculptra for correction of Midface Volume Deficit and/or Midface Contour Deficiency in subjects of Chinese origin, men or women aged 18 years or older.

For Group A, after screening, eligible subjects will be treated from day 1 and followed up for 24 months.

For Group B, the study includes two phases as follows:

Main study phase: It is randomized, evaluator-blinded and no-treatment controlled. After screening, all eligible subjects will be randomized either to the Treatment Group or the Control Group in a 2:1 ratio. All the subjects will be followed up for 12 months.

Extension study phase: After the main study phase, the Treatment Group and Group A will be followed up for additional 12 months.

Each Treating Investigator will enroll 1 or 2 subjects as Group A. Before start of enrolment into Group B, the injection technique will be evaluated by the Sponsor or designee of Sponsor and performed after the subjects in Group A for each investigator have received their first treatment and second treatment. If treatments are found to be correctly performed, no further training is needed, there are no outstanding questions regarding the injection technique and no other corrective actions are identified, the enrolment in Group B can start for that investigator.

Each subject assigned to Group A and Treatment Group will receive up to 4 injection sessions with 5 (± 1) weeks intervals. Study treatments should be stopped if optimal midface augmentation has been obtained or a maximum of 4 injection sessions completed. Optimal midface augmentation is defined as the best possible aesthetic result that can be obtained for an individual study participant, as agreed upon by the treating investigator and subject.

Subjects assigned to the Control Group will not receive treatment during the study.

For more details regarding the study, and references, see the Clinical Study Protocol (MA-39381).

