2.5.3 Adverse events

All AEs will be coded according to MedDRA.

A summary of all AEs, by Treatment Group, will be provided, which will include:

- Number of subjects with at least one AE and number of events (in total as well as serious AEs)
- Number of subjects with at least one related AE and number of events (in total as well as serious AEs)
- Number of subjects with at least one unrelated AE and number of events (in total as well as serious AEs)
- Number of subjects who did not have an AE.

Related AEs as well as number of subjects with related AEs will be summarised by SOC, PT and intensity. In addition, for related AEs the number of days to onset and the duration of event will be summarised by SOC and PT using mean, SD, min, max and median. Action taken for related AEs will also be summarized. Related AEs will be summarized per treatment session.

Serious AEs will be listed.

Late onset (>21 days) AEs will be listed.

Related AEs with late onset (>21 days after most recent treatment) will be listed, if any.

Non-related AEs will be summarised by SOC, PT, and intensity and by Treatment Group.

Time to onset of an AE will be derived as the start date minus the date of most recent treatment. For the Control group date of randomization will be used instead of most recent treatment. If the start date is missing, it will be assumed that the AE started on the day of most recent treatment. If the start month is available but not the day, it will be assumed that the AE started on the first day of the month.

Duration of an AE will be derived as the stop date minus the start date + 1. If the start date is missing, it will be assumed that the AE started on the day of most recent treatment or date of randomization for the Control group. If the start month is available but not the day, it will be assumed that the AE started on the first day of the month. If the stop month is available but not the day, it will be assumed that the AE stopped on the last day of the month. Completely missing stop dates will not be imputed and therefore no duration will be calculated in these cases. Instead, the number of AEs that were ongoing at the end of the study will be given.

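### The SAP's rules for incomplete adverse-event start dates can give negative, undefined or day-0 onset times, and onset is timed only from the most recent session

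*SAP*

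**What the plan says.** SAP 2.5.3 (Adverse events) sets four rules that matter here.

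- Definition: "Time to onset of an AE will be derived as the start date minus the date of most recent treatment". For untreated subjects, "For the Control group date of randomization will be used instead of most recent treatment".
- Wholly missing start: "If the start date is missing, it will be assumed that the AE started on the day of most recent treatment".
- Month-only start: "If the start month is available but not the day, it will be assumed that the AE started on the first day of the month". No lower bound at the treatment date is given, either for onset or where the rule is repeated for duration.
- Late-onset listing: "Related AEs with late onset (>21 days after most recent treatment) will be listed, if any".

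The same section handles stop dates differently. A wholly missing stop date is left unimputed and no duration is calculated.

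The results feed Table 3-46 (related events by session), Table 3-47 (onset, labelled as timed from the last treatment) and Table 3-48 (duration). Onset and duration are both named as safety endpoints in SAP 1.6. Under SAP 1.1.1, treated subjects "will receive up to 4 injection sessions with 5 (± 1) weeks intervals". Protocol 2.6 and 8.3.8 describe early nodules at 3-6 weeks after treatment, and add: "Delayed occurrences of subcutaneous nodules at the injection site (within 1–14 months post injection) have been reported".

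**The concern.** A start date placed before the injection that preceded the event is not a usable onset time, and the SAP has no rule for a negative value or for an event with no preceding treatment. It also does not say whether the most recent treatment is looked up against the imputed date or against the session that really came before the event. Two programmers could follow the text and assign the same event to different sessions.

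Setting a missing start to day 0 fixes the answer to the question that the late-onset listing asks. For a product whose named risks include delayed nodules, this matters for describing when events occur. At stake are onset, duration, session attribution and late-onset flags. Incidence is not at stake.

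**Working it through.** The documents give no figure to reproduce, so the rules were applied directly. Inputs: the SAP 2.5.3 rules; sessions 28-42 days apart, up to four (SAP 1.1.1); nodule windows of 3-6 weeks and 1-14 months (Protocol 2.6). Uniform gaps, calendar dates and onset times are assumptions.

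**1. Wholly missing start.** Onset = treatment date − treatment date = 0, and 0 > 21 is never true. Suppose four sessions 35 days apart, so the last is 3 × 35 = 105 days after the first. An event is first reported at Month 12 as new since Month 9. Its true onset lies between about 274 − 105 = 169 and 365 − 105 = 260 days after the last session. The SAP records 0.

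**2. Month-only start, by example.** Sessions fall on 8 September and 13 October (35 days apart). An event starts on 20 October and stops on 25 October, with only the start month recorded.

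- True onset: 20 − 13 = 7 days. True duration: 25 − 20 + 1 = 6 days.
- Imputed start: 1 October. Duration becomes 25 − 1 + 1 = 25 days.
- Measured from the session that preceded the event: 1 − 13 = −12 days.
- Measured from the session preceding the imputed date: 8 September to 1 October = 23 days, so it is listed as late onset and credited to session 1.

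**3. Month-only start, one session.** All injection dates over two years were enumerated (731 dates). The imputed start is on average 14.7 days too early (range 0-30).

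| True onset | Dated before the injection | Read as 21 days or less |
|---|---|---|
| Day 0 | 97% | 100% |
| Days 0-6 | 87% | 100% |
| Day 14 | 51% | 100% |
| Day 21 | 28% | 100% |
| Days 22-42 | 5% | 64% |
| 1-14 months (days 30-425) | 0% | 2% |

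**4. Month-only start, four sessions, event truly 0-20 days after a session (simulated).** 64% are dated before their own session and 16% before any treatment. If the anchor is looked up against the imputed date, 30% are moved to an earlier session and counted as later than 21 days. If the anchor is the session that really preceded the event, that share is 0%.

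**5. Timing from the most recent session, complete dates (simulated).** The fourth session falls on day 84-126 (3 × 28 to 3 × 42) after the first.

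- Events counted from session 1 at days 22-42, with a later session given: 38% fall after session 2 and are then at most 42 − 28 = 14 days from it.
- Events counted from session 1 at 1-14 months: 5.5%, 11% and 17% are read as 21 days or less with two, three and four sessions. With four sessions the median falls from 228 to 122 days.

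**The case against.** The strongest reply is that rules 1 and 2 may hardly ever operate. The eCRF has a start-date field for every AE and subjects are asked about AEs at each visit (Protocol 8.3.3). Monitors review every eCRF and raise queries (Protocol 9.2.2). That stands, and it is why no overall error rate can be given.

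Day 0 can also be defended as the cautious choice for attributing an event to treatment. That stands for causality, but not for finding late events. Timing from the last treatment is openly labelled in Table 3-47, and the data cannot show which of several sessions caused a nodule. That also stands: the convention is incomplete, not wrong.

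Four stronger readings are tempting, and the documents do not support them.

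- That nodules are hidden: each is recorded as an AE (Protocol 8.3.3), related events are tabulated by SOC and PT whatever their onset (SAP 2.5.3), and all CRF data are listed (SAP 2.1).
- That delayed nodules are often dated before the injection: from day 30 this does not happen in the single-session calculation. It is a problem of early events.
- That 30% of early month-only events become falsely late: this needs one of two readings that the SAP leaves open.
- That a missing start maximises duration: among the possible treatment dates, the most recent gives the shortest duration.

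**Conclusion.** The gap is real and minor. Followed literally, SAP 2.5.3 can give impossible or undefined onset for month-only dates in the injection month, overstates duration for month-only starts, and excludes every event with a wholly missing start from the related late-onset listing. The percentages are conditional on a date being incomplete and rest on uniform distributions. The actual number affected is unknown and could be very small.

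The single-clock point applies to complete dates as well, but its effect is bounded: 83-94% of events at 1-14 months from session 1 would still count as late. No hypothesis test uses any of these outputs.

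**What to change.** Amend SAP 2.5.3 before database lock, as SAP 2.1 allows.

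(a) Month-only start: use the later of the 1st of the month and the last treatment known to precede the event, judged from the visit at which it was reported, and never a later session. Use the same date for duration. Where the possible dates straddle a session or the 21-day cut-off, flag the event as not classifiable and include it, marked, in the late-onset listings.

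Both parts are needed. In the four-session simulation the floor brings negative onset to 0%. But among month-only events truly more than 21 days after the most recent session (drawn at 22-42 days), 71% would still be read as 21 days or less. The present rule gives 66-71%, depending on the anchor. A simpler floor at the last treatment in the month would be worse: it picks a session after the event for 16% of the early events and reads 87% of the late ones as 21 days or less.

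(b) Wholly missing start: calculate no onset or duration, as the SAP already does for missing stop dates. Count and list the event as onset unknown.

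(c) Table 3-47: add onset from first treatment beside onset from most recent treatment, at least for papules and nodules.

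The cost is a few lines of text and one column. A few events will have no numeric onset.

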**Effective**

Version: 2.0

or areas of induration have been noted in the injection area. Nodules are occasionally associated with inflammation or discolouration. The early occurrence of subcutaneous nodules at the injection site (within 3–6 weeks after treatment) may be minimised by adhering to proper dilution and injection techniques. Delayed occurrences of subcutaneous nodules at the injection site (within 1–14 months post injection) have been reported with sometimes a prolonged duration of up to 2 years.

For nodular areas or late granuloma formation, in some cases, they resolved spontaneously or following treatment with multiple intralesional injections of corticosteroids and/or antineoplastic agents (e.g. 5-fluorouracil). Surgical excision of the nodules was sometimes required when they were larger in size, occurring in difficult anatomical regions (e.g. lower eyelid) or persisting after other treatments.

Vascular compromise may occur due to an inadvertent intravascular injection or as a result of vascular compression associated with implantation of any injectable product. This may manifest as blanching, discolouration, necrosis or ulceration at the implant site or in the area supplied by the blood vessels affected; or rarely as ischemic events in other organs due to embolisation. Rare but serious cases of ischemic events associated with temporary or permanent vision impairment, blindness, cerebral ischaemia or stroke have been reported following facial aesthetic treatments.

By April 2018, Sculptra had marketing approval in 18 countries/regions worldwide, including US, EU, Canada, Australia, Hong Kong, Taiwan, South Korea, etc. Sculptra has been proven safe and well tolerated with sustained aesthetic improvement for facial lipoatrophy or volume loss. The primary potential benefit of the study is a perceived improvement in the treated areas. However, there is a risk that the subject will not gain the full aesthetic correction of Midface volume Deficit and/or Midface Contour Deficiency. There is also a risk of device dislocation.

Given the anticipated low level of acceptable adverse events (AE) in connection with the injection, the risk-benefit assessment of the use of Sculptra for treatment of Midface volume Deficit and/or Midface Contour Deficiency appears to offer a clinical benefit at reasonable risk.

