#### 3.2.3 Safety endpoints:

- Incidence, intensity, duration, and onset of adverse events (AEs) collected throughout the study.
- Incidence, intensity, and number of days of expected post-treatment events collected using 4-week subject diaries after each treatment session for the Treatment Group.

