### 8.3.6 Follow-up of Unresolved Events after study termination and new Events after study termination.

All serious as well as non-serious AEs with a causal relationship to the study product or treatment procedure and ongoing at study end, shall be followed up after the subject's participation in the study is over. Such events shall be followed-up after the last study visit until resolved, assessed as chronic or stable, or for at least three months. Final outcome after study end should be reported on a paper AE form.

All serious as well as non-serious AEs with a causal relationship to the study product or treatment procedure with onset after subject participation in the study has ended shall be collected and reported to Sponsor on a paper AE form or in the post marketing AE form or SAE paper form if applicable. The events shall thereafter be followed up until resolved or considered chronic or stable, or for at least three months. Final outcome shall be reported on the AE follow up form or in the post marketing AE form. The Investigator shall report any such AE or SAE including all previous Adverse events reported during the study and medical history of the patient to the Sponsor immediately but not later than 24 hours of awareness of the event. This report can be made via fax or e-mail according to contact details specified in section 8.3.5.

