Serious						
Non-serious						
Unrelated AEs, total						
Serious						
Non-serious						
Subjects with no AE reported						

$$\% = (n/N) * 100$$
Table 3-45: Related Adverse Events by MedDRA SOC and preferred term, Main study, subjects randomized to Sculptra, Safety population

Primary SOC	Preferred Term	Subjects		Events	Maximal Intensity		
		n	%		Mild	Moderate	Severe
Total							

$$\% = (n/number of subjects in the Safety population) * 100$$
Effective

Version: 1.0

	Title 43CHSA1803 Statistical Analysis Plan - Sculptra China	Doc id MA-40407
--	---	---------------------------

**Table 3-46: Related Adverse Events by MedDRA SOC and preferred term, by treatment session,
Main study, subjects randomized to Sculptra, Safety population**

Visit	Primary SOC	Preferred Term	Subjects		Events #	Maximal Intensity		
			n	%		Mild	Moderate	Severe
Baseline / Treatment 1								
Treatment 2 (optional)								
Treatment 3 (optional)								
Treatment 4 (optional)								

% = (n/number of subjects in the Safety population)*100

2019-10-24 08:59

Effective date:

Effective

Version: 1.0

**Table 3-47: Time to onset from last treatment of related AEs,
Main study, subjects randomized to Sculptra, Safety population**

Preferred term	Time to onset (days)					
	n	Mean	SD	Min	Median	Max
Total						

NA = Not Applicable

**Table 3-48: Duration of related AEs,
Main study, subjects randomized to Sculptra, Safety population**

Preferred term	Duration (days)					
	n	Mean	SD	Min	Median	Max
Total						

NA = Not Applicable

**Table 3-49: Action taken of related AEs,
Main study, subjects randomized to Sculptra, Safety population**

Preferred term	Action taken			
	None	Medication treatment	Non-pharmacological treatment or other procedures / tests	Withdrawn
Total				

**Table 3-50: Unrelated Adverse Events by MedDRA SOC and preferred term,
Main study, Subjects randomized to Sculptra, Safety population**

Primary SOC	Preferred Term	Subjects		Events #	Maximal Intensity		
		n	%		Mild	Moderate	Severe
Total							

% = (n/number of subjects in the Safety population)*100

 GALDERMA	Title 43CHSA1803 Statistical Analysis Plan - Sculptra China	Doc id MA-40407
--	---	---------------------------

2019-10-24 08:59

Effective date:

**Table 3-51: Unrelated Adverse Events by MedDRA SOC and preferred term,
Main study, Subjects randomized to no-treatment control, Safety population**

Primary SOC	Preferred Term	Subjects		Events #	Maximal Intensity		
		n	%		Mild	Moderate	Severe
Total							

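### The AE duration summary covers only events that have ended, so mean, median and maximum run short for long-lasting events such as delayed nodules

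*SAP*

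**What the plan says.** Protocol 3.2.3 (and SAP 1.6) makes duration part of the first safety endpoint: "Incidence, intensity, duration, and onset of adverse events (AEs) collected throughout the study".

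SAP 2.5.3 defines duration as stop date minus start date plus 1. A stop date with only the day missing is set to the last day of the month. For events with no stop date at all: "Completely missing stop dates will not be imputed and therefore no duration will be calculated in these cases". The next sentence adds: "Instead, the number of AEs that were ongoing at the end of the study will be given". For related AEs, "the duration of event will be summarised by SOC and PT using mean, SD, min, max and median".

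The shell "Table 3-48: Duration of related AEs" (Main study, subjects randomized to Sculptra) has columns for n, mean, SD, minimum, median and maximum by preferred term, and none for ongoing events. SAP section 3 plans the same tables, where applicable, for the extension phase, the combined phases and Group A. SAP 2.5.3 also lists related AEs that start more than 21 days after the most recent treatment.

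Protocol 2.6 and 8.3.8 put the onset of delayed nodules at 1 to 14 months after injection and say that they "have been reported with sometimes a prolonged duration of up to 2 years". Protocol 8.3.3 has papules and nodules recorded as AEs. Under Protocol 8.3.6, related events open at study end are followed until resolved, chronic or stable, or for at least three months: "Final outcome after study end should be reported on a paper AE form". The SAP does not say whether those dates reach any table.

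**The concern.** An event lacks a stop date at the data cut mainly because it has lasted until then. Dropping it is selection on the very quantity being summarised: short events stay, long ones leave, and the loss grows with true duration. For reactions that Protocol 2.6 expects to resolve in 2 to 6 days this does not matter. For nodules that can appear a year after injection and persist for up to two, it does, because follow-up ends 24 months after baseline and the first analysis comes at Month 12. A reader of Table 3-48 would take its mean, median and maximum as describing how long related events last, when they describe only those that ended in time.

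**Working it through.** The documents state no AE duration and no share of events ongoing, so there is no figure to reproduce. The check has a bound that needs no duration distribution and an illustration that needs one.

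**Inputs from the documents.** Up to four sessions 5 (±1) weeks apart (SAP 1.1.1), so nominally weeks 0, 5, 10 and 15. Delayed-nodule onset 1 to 14 months after injection, duration up to 24 months (Protocol 2.6, 8.3.8). Analyses when Month 12 is complete (SAP 2.6) and after Month 24. One month is taken as 30.4375 days, so week 15 = 15 × 7 / 30.4375 = 3.45 months.

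**Bound.** Longest duration that can be complete = cut − last session − onset. With the earliest delayed onset, 1 month after the last session:

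- Month 12: 12 − 0 − 1 = 11.0 months (one session); 12 − 3.45 − 1 = 7.6 months (four sessions).
- Month 24: 24 − 0 − 1 = 23.0 months (one session); 24 − 3.45 − 1 = 19.6 months (four sessions).

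The final visit may fall 4 weeks late. That adds 28 / 30.4375 = 0.9 month, giving 23.9 at best. Without dates from after the study, a delayed nodule that lasts the full two years cannot enter the summary at either cut, so even the maximum is truncated.

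**Illustration.** Assumptions: onset uniform over 1 to 14 months after the last session; duration exponential with parameter m = 3, 6 or 12 months, capped at 24. The true mean is m(1 − exp(−24/m)) = 3.0, 5.9 and 10.4 months.

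For a last session at L, the time left to a started event is uniform between lo = max(0, cut − L − 14) and hi = cut − L − 1. Then:

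- share excluded = m/(hi − lo) × [exp(−lo/m) − exp(−hi/m)]
- ended-only mean = {m − m/(hi − lo) × [(lo + 2m)exp(−lo/m) − (hi + 2m)exp(−hi/m)]} / (1 − share excluded)

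Example, four sessions, Month 24, m = 6: lo = 6.55, hi = 19.55. Share excluded = 6/13 × (0.336 − 0.038) = 14%. Ended-only mean = {6 − 6/13 × [18.55 × 0.3356 − 31.55 × 0.0384]} / 0.863 = 3.69 / 0.863 = 4.3 months, against a true 5.9.

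| Cut | Sessions | Excluded, m = 3/6/12 | Ended-only mean (months) | True mean (months) |
|---|---|---|---|---|
| Month 24 | one | 1 / 8 / 27% | 2.9 / 4.8 / 6.5 | 3.0 / 5.9 / 10.4 |
| Month 24 | four | 3 / 14 / 35% | 2.8 / 4.3 / 5.5 | 3.0 / 5.9 / 10.4 |
| Month 12 | one | 27 / 46 / 65% | 2.0 / 2.7 / 3.1 | 3.0 / 5.9 / 10.4 |
| Month 12 | four | 37 / 57 / 74% | 1.7 / 2.0 / 2.3 | 3.0 / 5.9 / 10.4 |

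The Month 12 rows apply only if stop dates are cut at Month 12. Simulation agrees with these figures to within a percentage point.

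For nodules starting 3 to 6 weeks after the fourth session, with a true mean of 5.9 months, the simulated ended-only mean is 3.0 at Month 12 and 5.2 at Month 24. For reactions lasting 2 to 6 days nothing is excluded at either cut.

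**Does censoring repair it?** A Kaplan-Meier median with open events censored at the cut returns the true medians of 2.1, 4.2 and 8.3 months in every row of the table but one case. For four sessions at Month 12 with m = 12, it is correctly not reached, because the longest follow-up (7.6 months) is shorter than the true median.

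**The case against.** The SAP does not hide open events. It commits to a count of those ongoing at study end, lists related AEs starting more than 21 days after treatment (which takes in every nodule starting a month or more after the last session), and provides all data in subject listings (SAP 2.1). Combined-phase tables are planned, and by Month 24 the shortfall is small for moderate durations. The protocol's wording, that nodules sometimes last up to two years, describes a tail, not a mean of 6 to 12 months. Sessions 2 to 4 are optional, so many subjects may have longer follow-up after their last injection than the four-session rows assume. No test or success criterion uses this table.

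All of that stands as a limit on size and seriousness. It does not remove the bias: a count and a listing leave the mean, median and maximum unchanged. The count also has no column in Table 3-48 and is defined only at the end of the study, not at Month 12. Protocol 8.3.3 has separate outcome codes for ongoing, chronic/stable and not recovered at study end, and the SAP does not say which of them count as ongoing.

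Three stronger readings are tempting, and the documents do not support them.

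- A reader might infer that the safety objective gets a falsely reassuring answer. With the count and the late-onset listing in the report, the defect is confined to the duration statistics.
- A reader might infer that this concerns the most important risk. Protocol 2.6 and 8.3.8 also name vision loss, stroke and necrosis, and rank none of them below nodules.
- A reader might take the Month 12 figures as certain. The SAP does not say that Main-study tables freeze stop dates at Month 12; if they are rerun later with updated dates, the shortfall shrinks.

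**Conclusion.** The concern holds as a bias in one descriptive summary of a stated safety endpoint. The direction is certain for events that can outlast follow-up. The size depends on durations that the documents do not give. Under the assumptions above, the ended-only mean at Month 24 is 92 to 97% of the truth when the true mean is 3.0 months (2.75/3.00 and 2.90/3.00), and 53 to 62% when it is 10.4 months (5.49/10.38 and 6.46/10.38). At Month 12 it could be as low as 22% (2.26/10.38) if stop dates are cut there. For injection reactions lasting days there is no effect, and the effectiveness conclusions are untouched. It should be corrected before database lock, but it does not threaten the trial.

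**What to change.** In SAP 2.5.3 and Table 3-48:

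1. Show the number ongoing at the data cut beside n for each preferred term.
2. Define ongoing at the Month 12 cut and at the final cut, including which recorded outcomes count.
3. Label the existing mean, SD, median, minimum and maximum as resolved events only.
4. At least for papules and nodules, and at least in the combined-phase table, add a Kaplan-Meier duration with ongoing events censored at the cut or last contact.

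The cost is a SAP amendment, which SAP 2.1 allows before database lock, and one reprogrammed table. Start dates, stop dates and visit dates are already collected. Reported durations will be longer, and the Kaplan-Meier median may not be reached for rare terms.

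Stop dates from the post-study paper forms could be given as a supplement where available, but the fix should not depend on them. They would need entry, reconciliation and a rule relative to database lock, and that follow-up may itself end without a stop date.
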